4.7.9 Postoperative period

Nasogastric tube will be removed after operation. Antibiotics will be given single dose. If gallbladder perforation with bile spillage is present, antibiotics will be given total three doses.

For postoperative pain control, regular analgesic with paracetamol suppository (750 mg for <50 kg and 1 G for \geq 50 kg body weight of the patient) will be given 6 hourly up to 72 hours. The patient will be assessed the pain score by using visual analogue scale (VAS) within 12 hour, 24 hour, 36 hour and 48 hour. Rescue analgesia will be added with injection of intravenous tramadol 1mg/kg if VAS was more than 4 and/or if the patient suffers breakthrough pain or if the patient complain of pain between the assessments. Total number and dose of rescue analgesia will be recorded in the proforma.

Patient will be discharged according to discharge criteria. The postoperative hospital stay will be calculated and recorded in proforma for each patient. During the hospital stay all cases will be observed daily by the researcher for early postoperative complications till the patients are discharged from the hospital. The complications which will be observed are wound infection, prolonged ileus, bile duct injury and bowel injury. Complications will be diagnosed clinically and confirmed by relevant investigations. These complications will be recorded in the proforma. All the complicated cases will be treated under the experienced consultant surgeon together with the researcher. After resuming oral intake, oral cefixime 200 mg twice a day will be given up to 5th postoperative day. Patient will be ordered to take oral paracetamol 500 mg if they feel pain after discharge.

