4.8.4 Intraoperative complications

Intraoperative complications include bile duct injury, bowel injury, vascular injury and injury to nearby structures.

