4.8.5 Bile duct injury

It means the injury to common bile duct with bile spillage during dissection of the Calot's triangle.

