5. DUMMY TABLES

Table 1. Age distribution in both study groups

No.	Age (Years)	Group A CLC		Group B TPPOP LC	
		No.	%	No.	%
1	<30				
2	31-40				
3	41-50				
4	51-60				
5	>60				
	Total				

Table 2. Sex distribution in both study groups

No.	Sex	Group A CLC		Group B TPPOP LC	
		No.	%	No.	%
1	Male				
2	Female				
	Total				

Table 3. Comparison of operation time between both study groups

Operation time (minutes)	Group A CLC		Group B TPPOP LC		P value
	No.	%	No.	%	
30 – 60					
61 – 90					
91 – 120					
>120					
Total					
Mean \pm SD					

Table 4. Comparison of intraoperative complications in both study groups

Intraoperative complications	Group A CLC		Group B TPPOP LC		P value
	No.	%	No.	%	
Bile duct injury					
Bowel injury					
Vascular injury					
Injury to nearby structures					
Others					
Total					

Table 5. Rate of conversion to open cholecystectomy in group A (CLC)

Conversion to other procedure	Group A CLC		P value
	No.	%	
Conversion to open procedure			
Total			

Table 6. Rate of conversion to other procedures in group B (TPPOP LC)

Conversion to other procedure	Group B TPPOP LC	
	No.	%
Conversion to CLC		
Conversion to open procedure		
Total		

Table 7. Comparison of rate of conversion to open procedure in both study groups

Conversion to open procedure	Group A CLC		Group B TPPOP LC		P value
	No.	%	No.	%	
Conversion to open					
Total					

Table 8. Postoperative pain assessment by VAS at 12 hour after operation

Severity of pain	Group A CLC		Group B TPPOP LC		P value
	No.	%	No.	%	
Mild					
Moderate					
Severe					
Total					

Table 9. Postoperative pain assessment by VAS at 24 hour after operation

Severity of pain	Group A CLC		Group B TPPOP LC		P value
	No.	%	No.	%	
Mild					
Moderate					
Severe					
Total					

Table 10. Postoperative pain assessment by VAS at 36 hour after operation

Severity of pain	Group A CLC		Group B TPPOP LC		P value
	No.	%	No.	%	
Mild					
Moderate					
Severe					
Total					

Table 11. Postoperative pain assessment by VAS at 48 hour after operation

Severity of pain	Group A CLC		Group B TPPOP LC		P value
	No.	%	No.	%	
Mild					
Moderate					
Severe					
Total					

Table 12. Rescue analgesic injection Tramadol requirement in both study groups

	Doses of Injection Tramadol requirement		P value
	Group A CLC	Group B TPPOP LC	
12 hour			
12 – 24 hour			
24 – 36 hour			
36 – 48 hour			
Total			
Mean \pm SD			

Table 13. Comparison of postoperative complications in both study groups

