Postoperative complications	Group A CLC		Group B TPPOP LC		P value
	No.	%	No.	%	
Wound infection					
Prolonged ileus					
Others					
Total					

Table 14. Comparison of duration of postoperative hospital stays in both study groups

Duration of postoperative hospital stay (days)	Group A CLC		Group B TPPOP LC		P value
	No.	%	No.	%	
≤3					
4- 7					
8-14					
>14					
Total					
Mean ± SD					

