7. APPENDICES

Appendix 1: Proforma

A. Identification

Case No. ()

Registration No -----

Name -----

Age -----

Sex Male Female

Body weight ----- kg Height ----- m² BMI (Kg / m²) -----

Address -----

Date of admission -----

Date of discharge -----

B. Operations

1. Date - ----- Time start - ----- Time end - -----

2. Operative time - () min

C. Intraoperative complications

Yes **No**

- | | | |
|--------------------------------|--------------------------|--------------------------|
| 1. Bile duct injury |  |  |
| 2. Bowel injury |  |  |
| 3. Vascular injury |  |  |
| 4. Injury to nearby structures |  |  |
| 5. Others |  |  |

D. Conversion to other procedure (Group A)

Yes **No**

[figure not shown]
Conversion to open

E. Conversion to other procedure (Group B)

[figure not shown]
Yes **No**

- | | | |
|-----------------------|--------------------------|--------------------------|
| 1. Conversion to CLC |  |  |
| 3. Conversion to open |  |  |

[figure not shown]
F. Postoperative pain assessment by VAS (Mild pain is 1- 4, moderate pain is 5 – 7 and severe pain is 8- 10)

[figure not shown]
1. 12 hr postoperative time Mild Moderate severe

2. 24 hr postoperative time Mild Moderate severe

3. 36 hr postoperative time Mild Moderate severe

4. 48 hr postoperative time Mild Moderate severe

G. Rescue analgesic requirement (Injection Tramadol)

	1 st Dose	2 nd Dose	3 rd Dose	4 th Dose	5 th Dose	6 th Dose	7 th Dose
Time							
Dose							

H. Postoperative complications

Yes

No

1. Wound infection

2. Prolonged ileus

3. Others

I. Duration of hospital stay - ----- days

[figure not shown]

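### Bile duct and bowel injury are watched for on the ward, but form, tables and definitions treat them as operative events, so their Table 4 rows can undercount them

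*Protocol*

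**What the plan says.** Section 4.7.9 (Postoperative period) has the researcher look daily for early postoperative complications until the patient goes home. It says: "The complications which will be observed are wound infection, prolonged ileus, bile duct injury and bowel injury". Diagnosis is clinical, with confirmation by investigations, and then: "These complications will be recorded in the proforma". It does not say which item of the form to use.

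The rest of the protocol places the two injuries elsewhere:

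- Section 4.8.4: "Intraoperative complications include bile duct injury, bowel injury, vascular injury and injury to nearby structures".
- Section 4.8.5, on bile duct injury: "It means the injury to common bile duct with bile spillage during dissection of the" Calot's triangle. Section 4.8.6 defines bowel injury in the same way, by escape of bowel contents in the course of the procedure.
- The proforma item headed "H. Postoperative complications" has three lines: wound infection, prolonged ileus, others. The two injuries appear by name only in item C, which is headed intraoperative.
- The shell titled "Table 13. Comparison of postoperative complications in both study groups" repeats those three lines and a total. The injuries have rows only in "Table 4. Comparison of intraoperative complications in both study groups".
- The variable list (4.9) carries bile duct injury (no. 7) and bowel injury (no. 8) as single Yes/No items with no time attached. It lists no variable for other complications.

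**The concern.** The protocol sets up a ward watch for two serious injuries, then gives the person completing the form no clear place to record one found there. Section 4.7.9 treats such a finding as a postoperative complication, but the postoperative item has no line for it other than 'Others'. The named line sits under an intraoperative heading and is governed by definitions that turn on spillage at surgery. Two careful recorders could file the same event differently.

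The definition of bile duct injury raises a related problem. A duct that is clipped, narrowed or damaged without bile escaping does not meet 4.8.5 as written, and neither does any injury to the common hepatic duct. Yet the operative steps in 4.7.4 and 4.7.5 have the surgeon identify the common hepatic duct in the same field.

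What is at stake is the safety comparison. The hypothesis (3.3) is that the two-port technique is as safe as the conventional one. The introduction describes bile duct injury as a serious threat to the patient. Objective 2 is reported in Table 4, the only table with a row for it.

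**Working it through.** **1. The texts side by side**

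| Place | Bile duct and bowel injury | How timed |
|---|---|---|
| 4.7.9 | Named among the complications watched for on the ward | Postoperative, to discharge |
| 4.8.4 | Named as intraoperative | Operation |
| 4.8.5, 4.8.6 | Defined by injury with spillage | During dissection or procedure |
| Proforma item C, Table 4 | Named lines | Headed intraoperative |
| Proforma item H, Table 13 | No named line; 'Others' available | Headed postoperative |
| 4.9, variables 7 and 8 | Yes/No | No time stated |

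No sentence says that item C is to be updated after surgery, and none sends a ward finding to 'Others'. Both entries are open.

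**2. The denominator**

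Section 4.5 gives 44 per group, and 49 after dropout. The check is (1.96 + 0.84)² × (0.79² + 1.02²) / (2.85 − 2.31)² = 44.75. The protocol takes this as 44, and 44 / 0.9 = 48.9, so 49. Rounding 44.75 up would give 45; that does not affect this point. I use 49 per arm.

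**3. Expected bile duct injuries per arm**

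Section 1.3 gives rates of 1% to 2% for the conventional technique and 1% to 3% for the two-port technique. I assume these describe all bile duct injuries, however recognised.

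- Conventional: 49 × 0.01 = 0.49 to 49 × 0.02 = 0.98.
- Two-port: 49 × 0.01 = 0.49 to 49 × 0.03 = 1.47.

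If an arm has any such injury, the chance that it has exactly one is P(X = 1) / P(X ≥ 1), with X binomial:

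- 1%: 0.3025 / 0.3889 = 78%
- 2%: 0.3716 / 0.6284 = 59%
- 3%: 0.3407 / 0.7752 = 44%

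**4. What one displaced event does to the row**

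- Counted: 1/49 = 2.0%, exact 95% interval 0.05% to 10.9%.
- Not counted: 0/49, exact 95% interval 0 to 7.3%.

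Significance does not move. Fisher's exact test, two-sided, 49 v 49, gives P = 1.00 for 0 v 1, P = 0.49 for 0 v 2 and P = 1.00 for 1 v 2.

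**5. What cannot be computed**

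The expected number missing from the row through filing is the expected number of injuries, times the share first recognised on the ward, times the share of those entered under 'Others'. The protocol gives neither share. The product can lie anywhere from 0 to the full 0.49 to 1.47 per arm. The share of duct injuries without spillage, or at the common hepatic duct, is not given either. No rate at all is given for bowel injury, so nothing is computed for it.

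**The case against.** The best reply is that the definitions date the injury and not its recognition. A duct cut at operation and diagnosed on day 2 was still injured during dissection, so it belongs in item C. The variable list supports this: one untimed Yes/No item for each injury, and no variable for other complications. The form also carries the discharge date and length of stay, so it stays open after surgery. This reading is sound and available. It defeats any claim that a ward finding would by default go under 'Others'. It does not settle the matter, because no text directs the entry to item C, 4.7.9 itself groups the injury with postoperative complications, and the named line carries an intraoperative heading. Nor does it help an injury without spillage or one to the common hepatic duct.

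A reader might also infer that 4.7.8 and 4.8.9 confine postoperative complications to infection and ileus and so shut the injuries out. They do not: both are worded as open lists.

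Nor do the figures in the working measure misfiling. The 44% to 78% range is the chance that an arm's injuries number exactly one, given at least one. It shows how fragile the row is, not how often the problem would occur.

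Finally, simply deleting spillage from the definitions would go too far. For bowel injury it would remove the only stated threshold and count trivial damage to the bowel wall. The fix below keeps a threshold.

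**Conclusion.** The mismatch between the ward watch in 4.7.9 and the form, tables and definitions is certain from the text. Its consequence is less certain: an injury first recognised on the ward may be entered in either of two places, and the literal wording of 4.8.5 leaves some duct injuries out. The Table 4 row for the key safety event can therefore be too low.

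The size is limited but not trivial. With about 0.5 to 1.5 bile duct injuries expected per arm, one event can be the whole count, and the row would then read 0/49 in place of 1/49. This rests on the rates in section 1.3 and on 49 patients per arm.

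Three stronger conclusions might be drawn, and the protocol supports none of them. The event is not lost, since item H and Table 13 have a line for others. The test result would not change at counts this small. No arm is shown to be favoured, because the same wording applies to both. The point is worth correcting before data collection, and it does not undermine the design.

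**What to change.** 1. **Counting rule.** State that a bile duct or bowel injury caused at operation counts in variables 7 and 8 and in its named table row whenever it is recognised up to discharge, with each patient counted once per injury.
2. **Section 4.8.5.** Cover the common bile duct or the common hepatic duct, with a bile leak, or with injury or obstruction confirmed by investigation or at reoperation.
3. **Section 4.8.6.** Keep a threshold: spillage or leak seen at operation, or perforation confirmed by investigation or at reoperation up to discharge.
4. **Proforma item H.** Add a Yes/No line with the date of recognition for each of the two injuries.

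The cost is one added sentence, two reworded definitions and two form lines. No visit, test or staff time is added, because 4.7.9 already provides daily observation and confirmation by investigations. The downside is that the counted rate may be higher than under the present wording, by the same rule in both arms.

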4.6.1 Inclusion Criteria

All patients with symptomatic gall stones who will be treated by laparoscopic cholecystectomy.

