4.6.2 Exclusion Criteria

4.6.2.1 Patients with ASA III, IV & V

4.6.2.2 Previous upper abdominal surgery

4.6.2.3 Patients with common bile duct pathology

4.6.2.4 Patients with clinical or USG suspected gall bladder cancer

4.6.2.5 Patients with bleeding disorders

4.6.3 Randomization procedure

Randomization will be done by block design in this study. The patients will be enrolled into the study according to inclusion and exclusion criteria. Then they will be randomized by block randomization method. For sample size of 98 in total, there will be 10 blocks, each having 10 patients. In each block with 10 cases, two methods will be allocated in random order. Random block design will be generated by using Graphpad Prism Software. The first case will be allocated into one block by envelope method. Then following 9 cases will go into the same block in order. After completing one block, the same procedure will be done for another block for 10 patients. The blocks used for this randomization is shown below.

1 2 3 4 5 6 7 8 9 10

Block1	A	A	B	B	B	A	A	B	A	B
--------	---	---	---	---	---	---	---	---	---	---

Block2	A	B	B	A	B	B	A	B	A	A
--------	---	---	---	---	---	---	---	---	---	---

Block3	A	A	B	B	A	B	B	A	A	B
--------	---	---	---	---	---	---	---	---	---	---

Block4	B	A	A	B	B	A	A	B	B	A
--------	---	---	---	---	---	---	---	---	---	---

Block5	B	A	B	A	A	A	B	B	A	B
--------	---	---	---	---	---	---	---	---	---	---

Block6	B	B	A	B	B	A	A	A	B	A
--------	---	---	---	---	---	---	---	---	---	---

Block7	A	A	B	A	A	B	A	B	B	B
--------	---	---	---	---	---	---	---	---	---	---

Block8	A	B	A	B	B	B	A	B	A	A
--------	---	---	---	---	---	---	---	---	---	---

Block9	B	A	B	A	A	B	B	A	A	B
--------	---	---	---	---	---	---	---	---	---	---

Block10	B	B	A	A	B	A	B	A	B	A
---------	---	---	---	---	---	---	---	---	---	---

Method A : Conventional laparoscopic cholecystectomy (CLC)

Method B : Two ports plus one puncture laparoscopic cholecystectomy (TPPOP LC)

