4.7 Research procedure

4.7.1 Patient selection and data collection

The study population will include those patients with symptomatic gall stones who will be treated by laparoscopic cholecystectomy in No.(1) Military Hospital (700 bedded) and will not be met the exclusion criteria. Complete history will be taken including patient's identification, presenting symptoms, past medical and past surgical history. Thorough physical examination including general and abdominal examination will be performed. Investigations including liver function test, complete blood picture, urea, creatinine, viral serology for preoperative assessment will be done. Abdominal sonography will be carried out. The results will be recorded in the proforma.

After selection of the patients by inclusion and exclusion criteria, eligible patients will be counseled by the author about nature of disease, type of operation to be performed and possible complications. If the patient agrees to participate, a written informed consent will be obtained. The participants will be randomly allocated by block randomization method. Method A conventional laparoscopic cholecystectomy (CLC) will be done for control group and Method B two ports plus one puncture laparoscopic cholecystectomy (TPPOP LC) will be done for study group.

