4.7.2 Preoperative preparation

The patients will be reviewed by anesthetist for preoperative assessment. General anesthesia will be required for both types of procedure. All patients will be entailed fasting for 6 hours. Prophylactic antibiotics will be given as intravenous ceftriaxone 1G at induction of anesthesia in both methods. If the patient has cephalosporin hypersensitivity, fluoroquinolones group like levofloxacin 500mg will be given. A nasogastric tube will be inserted at induction of anaesthesia to decompress the stomach in both study groups. The patient will be asked to void urine immediately prior to surgery. The patient will be placed in supine position in both study groups (**Fig 10**). The entire abdomen will be cleaned and draped in standard sterile fashion.

[figure not shown]

Figure 10. Operation table set up for laparoscopic cholecystectomy (Kumar et al, 2017)

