4.11 Ethical Consideration

This study will be considered to be ethical because the following conditions will be fulfilled for the research.

- (i) The individual will be invited for the voluntary in the research.
- (ii) The individual is free to refuse to participate and will be free to withdraw from the researcher at any time without penalty or loss of benefits to which he or she would otherwise be entitled.
- (iii) The aim and procedure of research will be clearly explained and written informed consent will be taken before the initiation of the research work.
- (iv) The potential patient will be explained the issue understanding about the following:
 - (a) The expected duration of the individual's participation
 - (b) The individual's participation is voluntary only, not for money or other forms of materials in return for the participation.
 - (c) Both methods are the international accepted options for management of symptomatic gall stones.
 - (d) Although accepted procedure, it still has chance of complications like wound infection, pain, bleeding and injury to nearby organs, etc.
 - (e) To prevent the infection, potent broad spectrum antibiotics will be given before procedure intravenously after test dose.

- (f) Pain can be present and will be treated according to pain treatment guideline in methodology.
- (g) Complications of other will be treated accordingly.
- (h) Researcher will take the responsibility for scientific correctness in conducting research according to protocol, not allowing scientific misconduct and confidentiality for all the information and results in this study.
- (i) For the injuries or complications associated with research, the patient will be given immediate appropriate comprehensive treatment without patient's expense.
- (j) There will be no compensation for participation in the research because participation in the research is completely voluntary.
- (k) There will be no conflict of interest from any Instrument Company or Pharmaceutical Company.
- (l) The protocol will be submitted to the Institutional Ethical Review Committee to approve or clear the protocol.

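### Section 4.7.9 orders oral cefixime to day 5 without the cephalosporin-hypersensitivity exception that section 4.7.2 writes for ceftriaxone: a minor patient-safety inconsistency

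*Protocol*

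**What the plan says.** - **Intravenous prophylaxis, protocol 4.7.2:** "Prophylactic antibiotics will be given as intravenous ceftriaxone 1G at induction of anesthesia in both methods". The next sentence adds the exception: "If the patient has cephalosporin hypersensitivity, fluoroquinolones group like levofloxacin 500mg will be given".
- **Eligibility, protocol 4.6.1 and 4.6.2:** the single inclusion criterion is "All patients with symptomatic gall stones who will be treated by laparoscopic cholecystectomy". The five exclusions cover ASA class III to V, earlier upper abdominal surgery, common bile duct pathology, suspected gallbladder cancer and, last, "Patients with bleeding disorders". None concerns drug hypersensitivity.
- **Oral course, protocol 4.7.9:** once the patient is eating and drinking again, "oral cefixime 200 mg twice a day will be given up to 5th postoperative day". No exception and no alternative drug follow.
- **Steps that could identify a hypersensitive patient:** the history in 4.7.1 covers "presenting symptoms, past medical and past surgical history". In 4.7.2, "The patients will be reviewed by anesthetist for preoperative assessment". Item (e) of the information given to patients under 4.11 says that "potent broad spectrum antibiotics will be given before procedure intravenously after test dose".

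**The concern.** The protocol foresees hypersensitive participants and has a rule for them, but it writes that rule for one of the two cephalosporins it orders. The other is the longer exposure: twice-daily dosing to day 5, against one dose of ceftriaxone at induction. Discharge under 4.8.16 depends on meeting criteria and not on a fixed day, so part of the oral course may be taken at home, after the researcher's daily observation has ended.

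What is at stake is the safety of individual participants and the consistency of a treatment instruction. A statistical analysis plan would not supply this rule. Antibiotic orders belong in the protocol, and this one is stated there incompletely.

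**Working it through.** The protocol has no figure to reproduce on this point, and no formula applies. The check compares the sections.

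**1. Can a hypersensitive patient be in the trial?** Yes. The inclusion criterion in 4.6.1 is unrestricted in this respect, and 0 of the 5 exclusions in 4.6.2 concern drug hypersensitivity. The exception in 4.7.2 also presupposes that such patients are treated.

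**2. Which cephalosporins are ordered, and which carry the exception?**

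| Section | Drug | Timing | Exception stated |
|---|---|---|---|
| 4.7.2 | Ceftriaxone, intravenous | Induction of anaesthesia | Yes: fluoroquinolone instead |
| 4.7.9 | Cefixime, oral | From oral intake to postoperative day 5 | No |

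That is 1 exception for 2 orders. The protocol does not say that cefixime is a cephalosporin; this is general drug-class knowledge. No claim about cross-reaction between the two drugs is needed, because 4.7.2 defines its exception by class and not by drug.

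**3. Does another section carry the exception to cefixime?** None does. The test dose in 4.11 is tied to the intravenous drug before the procedure. It may reveal a reaction, but it sets no rule for the oral course. The history and the anaesthetist's review likewise identify the patient without saying what to give afterwards. The exception in 4.7.2 names no oral course and no duration, so a reader who extends it to 4.7.9 still has to decide what to prescribe.

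**4. Who receives cefixime?** This is unclear. The order follows a sentence on the care of complicated cases and precedes one on pain relief after discharge for patients in general. If it applies to everyone, up to 49 + 49 = 98 planned patients receive it (sample size from 4.5). If it applies to complicated cases only, fewer do. The exception is missing on either reading.

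**5. How many are affected?** This cannot be derived. The number affected is the number of cefixime recipients times the proportion who are hypersensitive. The first is known only to be at most 98, and the protocol does not give the second.

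**The case against.** The strongest reply is that hypersensitivity belongs to the patient and not to one order. The condition in 4.7.2 is worded that way, and a patient who meets it has been moved off the class before any oral drug is due. History, anaesthetist's review and test dose all come before the cefixime, and the same hospital team continues the care. Withholding a drug from a patient known to be allergic to it is ordinary prescribing. Section 4.7.9 also orders paracetamol and tramadol with no allergy clause, and nobody would call that a fault.

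Much of this stands. It makes actual administration unlikely and limits the point to a minor one. It does not remove the point, because for this class the authors did not rely on ordinary practice: they wrote a rule at the first order and omitted it at the second. Paracetamol and tramadol differ in that the protocol states no precaution for them anywhere.

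Three stronger readings are tempting, and the document supports none of them:

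- **That the protocol directs staff to override a known allergy.** It is silent at the second order. It does not revoke the first rule.
- **That 98 patients are at risk.** That figure is the ceiling on cefixime recipients, not the number of hypersensitive patients.
- **That the wound-infection comparison is biased.** The antibiotic instruction does not differ by arm, and nothing in the text suggests a differential effect.

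**Conclusion.** The omission is real and rests on the text alone: 4.7.9 orders a second cephalosporin without the exception in 4.7.2, for patients whom 4.6.2 does not exclude. It is a minor patient-safety inconsistency. Confidence in the omission is high. No size can be put on its consequence, so neither a count of affected patients nor a claim that they are few is offered.

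The conclusion assumes that cefixime is a cephalosporin and that 4.7.9 is followed as written. Clinicians would probably depart from it for a known hypersensitive patient. Sample size, error rates, randomization and the comparison between arms are not affected.

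**What to change.** Add one sentence to 4.7.9:

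> Patients with cephalosporin hypersensitivity, by history or at the test dose, will not receive cefixime; they will receive an oral fluoroquinolone in line with 4.7.2, or no oral course if that is contraindicated, by the same rule in both arms.

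The cost is that sentence. Sample size, randomization and analysis stay as they are. The clinical lead should settle the oral agent, dose and duration.

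A sixth exclusion criterion is the weaker alternative. It would narrow a population that 4.7.2 already provides for, and it would miss a reaction first seen at a test dose given after enrolment.

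Three drafting points could be settled in the same edit, but are optional: say which patients receive the oral course, say whether the single-dose and three-dose statements in 4.7.9 refer to the intravenous drug only, and add a line for drug hypersensitivity to the proforma in Appendix 1.
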